2. SPECIFIC AIMS

Primary Aim: Test the hypothesis that TRIUMPH intervention participants will have higher rates of biochemically validated, 7-day point-prevalence smoking abstinence at 18 months than TAU participants.

Secondary Aims:

1. Determine the effect of the TRIUMPH intervention compared to TAU on other CVD risk behaviors and factors:
 - a. Continuous smoking abstinence;
 - b. Weight and Body Mass Index;
 - c. Physical fitness with 6-minute walk test;
 - d. Healthy diet by self-report;
 - e. 10-year risk of cardiovascular events with the Global Framingham Risk Score;
2. Determine the effects of the TRIUMPH intervention on patient-reported and other outcomes: health status (SF-12); quality of life (Euroqol); psychiatric symptoms (BPRS); and acute care visits and hospitalizations;
3. Evaluate potential mediators of outcome (e.g., intervention attendance, text-messaging use, quit attempts, pharmacotherapy), and explore outcomes in selected subgroups of interest at baseline (e.g., those willing to set a quit date in 1 month, psychiatric diagnosis).
4. Assess costs per participant and cost-effectiveness incorporating long-term changes in CVD risk.
6. Assess factors that could facilitate implementation, and plan for future implementation and dissemination.

Protocol: Trial of Integrated Smoking Cessation, Exercise and Weight Management in SMI

Improving smoking abstinence, physical activity, diet and weight is critical to decrease premature CVD mortality in SMI, and will require innovative, integrated interventions in community settings. The TRIUMPH Trial will test such an approach that reaches a broad range of smokers with SMI and is practical to implement.

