Intervention Measures: In active intervention participants, to measure interim progress towards goals, inform case management and analyze potential mediators: we will track 1) attendance at integrated groups, individual visits, exercise classes (staff report) and gym use (sign-in records), 2) self-reported smoking since last visit expired CO, 3) study medication use by self-report/interim pill counts, 4) weights from weigh-ins and text responses, and 5) texting use (% completed responses, smoking and eating behavior, weight, daily steps).

Interviews: We will use a purposive sample of active intervention participants, and we will conduct interviews after the 18-month intervention to gain an understanding of participant perceptions of and satisfaction with the program.

Organizational factors (Substudy of factors related to intervention implementation): To better understand factors influencing implementation of the intervention and potential future dissemination, we will conduct semi-structured interviews with selected community mental health program leadership and staff, psychiatrists and health coaches with involvement in the intervention, and targeted (N=50), and we also will survey more widely mental health staff and clinicians at mental health programs (N=150). Interviews will ask about the intervention's perceived effectiveness, ease, associated barriers, fit within the organization and financial models for continued support. We will discuss issues around physician prescribing of smoking cessation pharmacotherapy. We will interview before the intervention and then at end of study to assess changes due to the intervention. Surveys will focus on assessing implementation climate and attitudes towards evidenced-based practices, perceptions of the role of various sectors of the health care and social services system in addressing clients' somatic health needs; perceptions of the TRIUMPH intervention, its usefulness; barriers to implementation; stigma toward persons with SMI; and patient communication. We will gain an understanding of factors impacting intervention acceptability, feasibility and future sustainment, and prepare groundwork for dissemination. Study team members will conduct interviews in person and administer surveys using Qualtrics or paper.

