Relapse prevention phase. Participants join this phase when they achieve ≥14 days biochemically confirmed continuous abstinence at the end of the 7-week smoking cessation phase. Sessions focus on learning and applying key cognitive and behavioral skills to high-risk situations, including refusal skills, problem-solving, identifying and responding to permission-giving beliefs, and developing and implementing personalized relapse prevention plans. Weight management strategies for high-risk situations and problem solving will be integrated throughout. (Tables 3, 4). Those who slip or resume smoking will be asked to remain in the group with the goal of regaining abstinence through subsequent supported quit attempts.

Individual sessions with the health coach will focus on reviewing progress and problem solving to enhance participants' strategies for smoking cessation and weight management. The coach will review relevant process data tailored to individuals' needs (e.g., expired CO, study session participation, gym use, use of texting, medication adherence, expired CO, weight, and step counts), and using motivational interviewing, will provide feedback and address readiness to adopt further changes. The potential synergistic effects of efforts to achieve goals across more than one type of health behavior will be discussed and reinforced as appropriate. Additional sessions may be scheduled for those not ready to set a quit date after 2 cycles of the 4-week motivational enhancement program or for those who do not achieve 2-week abstinence after 2 7-week active smoking cessation cycles. These participants will continue to participate in all other aspects of the intervention, and will be reassessed and encouraged to rejoin the appropriate group when ready.

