Exploratory Analyses: (Aim 3) We will explore for the potential of treatment effect differential between the participants who are ready to set a quit date within 30 days at baseline and those who are not. This analysis will be conducted under the intention to treat principle and will involve stratified analysis or statistical modeling invoking an interaction term between the status of setting the quit date and the parameter capturing the intervention effect. The trial is not powered to detect such an interaction but the result should be informative for future intervention and trial design. For other subgroups of interest defined at baseline (e.g., psychiatric diagnosis), we will adopt a similar analytic approach. In addition to analyses that preserve the intention to treat principle, we will perform informative exploratory analyses based on subgroups defined post-randomization to characterize aspects of the intervention that may be related to improved abstinence, weight, fitness and psychiatric outcomes in the active group. Such analyses will use post-randomization variables that are potential mediators –e.g., group and individual session visit and exercise class participation, specific pharmacotherapy use and adherence, and text-message self-monitoring activities.²²⁵ Even so, these analyses are more prone to biases because protection from confounding afforded by randomization is not likely applicable. Propensity score stratifications will be used to manage potential confounding in these analyses. Nevertheless, these findings will be interpreted with caution and will be considered exploratory.

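### Group sessions offered depend on having already quit, so a full-period count of groups attended can track abstinence even if groups have no effect

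*Combined protocol and SAP*

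**What the plan says.** Section 2 (Secondary Aim 3) sets out to "Evaluate potential mediators of outcome (e.g., intervention attendance, text-messaging use, quit attempts, pharmacotherapy" and similar variables. Section 13 (Exploratory Analyses, Aim 3) carries this out within the active group: "Such analyses will use post-randomization variables that are potential mediators". Among these it names "group and individual session visit and exercise class participation". It gives no attendance metric, no time window and no ordering of attendance before outcome. It accepts that randomisation does not protect these analyses, labels them exploratory, and offers one remedy: "Propensity score stratifications will be used to manage potential confounding in these analyses". The covariates are not named.

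Section 10 ties the group schedule to progress. For relapse prevention: "Participants join this phase when they achieve ≥14 days biochemically confirmed continuous abstinence at the end of the 7-week smoking cessation phase". Table 3 then gives weekly groups for a month, biweekly for the next, and monthly to the end of the study. Participants who do not become ready, or do not quit, finish their 4-week or 7-week courses and continue with individual work, with encouragement to rejoin. Individual and exercise sessions have one schedule for all phases, with a possible addition: "Additional sessions may be scheduled for those not ready to set a quit date after 2 cycles" of motivational groups, and likewise for those not abstinent after two cessation cycles. Section 7 confirms that staff log "attendance at integrated groups, individual visits, exercise classes (staff report") in the active arm.

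**The concern.** Relating attendance to outcome assumes that attendance comes first. Here, reaching abstinence opens a further stream of groups, while failing to reach it ends the scheduled ones. Someone who quits early and attends half of what is offered can build up more group visits than someone who does not quit and attends just as faithfully. The count then partly records the outcome.

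Section 13's caution concerns confounding, meaning differences between people who attend more and people who attend less. This dependence has another source: the schedule responds to an event after randomisation. Strata built from baseline variables would not remove it. At stake is what Aim 3 says about which components go with abstinence. A reader could credit the groups with a pattern that the timetable produced.

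**Working it through.** The plan gives no power or effect figure for this analysis, so there is none to reproduce. The check has three steps.

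**1. Groups offered, from Table 3 and Section 10.** Inputs: 18 months = 78 weeks; one month = 78/18 = 4.33 weeks; 4 weekly groups per motivational course; 7 per cessation course; relapse prevention 4, then 2, then 1 per month.

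Quits in the first course: monthly groups = (78 − 7 − 8.67)/4.33 = 14.4, so 14. Total = 7 + 4 + 2 + 14 = 27. The other pathways follow in the same way.

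| Pathway | Two courses at most | Three courses at most |
|---|---|---|
| Quits in course 1 | 27 | 27 |
| Quits in course 2 | 14 + 6 + 12 = 32 | 32 |
| Quits in course 3 | not applicable | 21 + 6 + 11 = 38 |
| One motivational course, then quits in course 1 | 11 + 6 + 13 = 30 | 30 |
| Never ready | 2 × 4 = 8 | 12 |
| Ready at baseline, never quits | 2 × 7 = 14 | 21 |
| Ready later, never quits | 4 + 14 = 18 to 8 + 14 = 22 | up to 12 + 21 = 33 |

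With two courses the ranges for quitters and never-quitters do not meet. With three they overlap (33 against 27). A fourth cessation course would offer a never-quitter 4 × 7 = 28, also above 27.

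**2. Other sessions.** Individual visits: about 6 in the first 3 months plus 15 monthly = 21. Exercise: 78 × 2 = 156 to 78 × 3 = 234 classes. Neither depends on quitting.

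**3. Simulation with no effect of sessions.** From the documents: 110 active participants (220 in equal allocation), 50% ready at baseline, 42% becoming ready per motivational course. Assumed: quit probability 0.20 to 0.43 per cessation course; 18-month abstinence of 30 to 50% after relapse-prevention entry and 2 to 10% without it; mean attendance of 30 to 70% of sessions offered, independent of quitting; no rejoining. Each scenario had 800 trials. Groups attended were compared by 18-month abstinence with a Wilcoxon test at 5%.

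- Two courses, quit probability 0.25, abstinence 45% after entry and 2% without, attendance 50%: overall abstinence was 17.5%. Abstainers attended 14.9 groups against 9.0. Abstinence was 27.5% in above-median attenders and 8.6% in the rest. The test rejected in 88% of trials, and in 87% after stratifying by baseline readiness.
- All scenarios: rejection in 30 to 97% with two courses and 12 to 77% with three.
- Attendance in the first four groups, or sessions attended divided by sessions offered: about 4 to 7%.
- Visits on the common 21-visit individual schedule: about 4 to 6%.

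A further set of runs added rejoining, with quit rates set to keep abstinence near 17 to 21%:

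| Rejoining | Two courses | Three courses |
|---|---|---|
| None | 91% | 53% |
| 30% chance at each opportunity | 37% | 14% |
| 60% chance | 6% | 7% |
| Continuous repetition | 43% | 44% |

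In the two-course run with continuous repetition the sign reversed: 11% abstinent in above-median attenders against 23% in the rest. These figures depend on how rejoining is modelled. The early-window measure stayed at 4 to 7% throughout.

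**The case against.** The strongest reply is that Section 13 never says it will use a raw count. That is correct, and the point is conditional on it: a full-period count is one natural reading of an undefined variable, and it is the reading that fails.

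Second, the split between quitters and non-quitters is looser than the two-course counts suggest. Section 10 lets non-progressors repeat curricula as needed, encourages rejoining, and keeps relapsers in the relapse-prevention group. This also stands. It makes the size and sign of the artefact uncertain, and with enough rejoining it can nearly vanish.

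Third, the analysis is already called exploratory and bias-prone. That limits the consequence, but it does not tell a reader that the timetable alone can produce the association.

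Fourth, dividing attended by offered sessions over the whole period would suffice, and a four-week window discards the maintenance attendance that motivates an 18-month design. The loss is real. However, the full-period share behaved well in the simulation because willingness to attend was drawn independently of quitting. In practice, attendance after a quit may itself respond to the quit, so the share is better kept descriptive.

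A reader might also infer that individual visits will look harmful because extra ones go to non-progressors. The documents do not support this. The scheduled visits are the same for everyone, and the extra ones only may be arranged.

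**Conclusion.** The concern holds for group sessions, conditionally. If Aim 3 uses a full-period count of groups attended, that count is partly a consequence of abstinence and can be associated with it when groups have no effect. The session counts come from Table 3 and Section 10. The rejection rates are illustrative, because the quit, retention, attendance and rejoining rates are assumptions. Propensity stratification on baseline variables would not remove the dependence; the plan does not say which variables it would use.

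Scheduled individual and exercise sessions do not carry the artefact; only the optional extra individual visits could. It would go too far to infer that the analysis is bound to show a spurious benefit, since the metric is open and repetition can shrink or reverse the pattern. Nor do the documents support any effect on the primary analysis, the sample size or the randomised comparisons. This is a worthwhile, inexpensive clarification of an exploratory analysis.

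**What to change.** In Section 13, Exploratory Analyses (Aim 3):

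- Define group attendance as the share of sessions offered in a fixed early window that closes before the schedule can depend on abstinence. The first four weekly groups would serve: both entry phases offer them, and entry to relapse prevention is decided only at the end of the 7-week phase.
- Stratify by baseline readiness and relate this share to 18-month abstinence. Keep propensity stratification for ordinary confounding, and name its covariates.
- Report full-period group attendance only as sessions attended divided by sessions offered, and only descriptively.
- Count optional extra individual visits separately from scheduled ones.

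The number of sessions offered depends on how many courses are allowed. Table 3 permits each course to be repeated up to twice; the text of Section 10 refers in different places to repeating as needed, to a second motivational course, and to two 7-week cycles. These need to be reconciled.

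The cost is SAP wording and a derived variable from attendance logs already kept. The inferential result would then speak only to early engagement, not to later attendance.

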3. BACKGROUND AND SIGNIFICANCE

Public health burden of tobacco smoking in persons with SMI

Nicotine dependence remains epidemic in adults with SMI, with smoking prevalence and resulting smoking-related mortality 2 to 5 fold higher than in the general population.^{14,36-44} One provocative estimate suggests 45% of all cigarettes in the US are sold to those with a mental illness.³⁶ Compounded by the strikingly higher prevalence of all CVD risk factors in SMI,^{45,46} smoking represents a major, neglected public health problem in this vulnerable population.^{12,25,47}

Benefits of smoking cessation

Smoking cessation dramatically reduces CVD mortality. After only 1 year of abstinence, myocardial infarction risk is reduced by 50%, and cessation in mid-life abrogates 90% of smoking-associated mortality risk.⁴⁸⁻⁵⁰ Smoking cessation treatments tailored to those with SMI are needed.⁴⁷

Short-term interventions for smoking cessation in SMI.

A recent Cochrane review²⁴ based largely on trials conducted by Drs. [name] and [name],^{26,27,29,51-54} found pharmacologic + behavioral interventions effective and behavioral treatment alone ineffective for smoking cessation in schizophrenia. The 2009 Schizophrenia PORT guidelines,^{55,56} for the first time recommended pharmacotherapy (bupropion +/- NRT) + behavioral treatment for those wanting to quit.^{26,27,29,51-54,57,58} Since the PORT, varenicline has been found effective for abstinence and well-tolerated in smokers with schizophrenia, bipolar disorder and depression(B1f).^{24,29,30,59-68} While pharmacotherapy has been found to be effective for smoking cessation in major depressive disorder (MDD), including a large study in depressed smokers by [name],⁶⁹ more work is needed in schizophrenia, bipolar disorder and recurrent MDD, consistent with SMI. The planned intervention is appropriate for the range of diagnoses included in SMI.

Smoking is a chronic illness

Relapse rates are high shortly after discontinuing pharmacotherapy,²⁴ with some trials reporting 50% relapse by 3 months, most occurring within 2 weeks.⁵¹ The average smoker makes 5 attempts before sustained abstinence,⁷⁰ so multiple tries after relapses should be expected and encouraged. This 18-month trial will address nicotine dependence as a chronic relapsing disorder in SMI.

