Maintenance interventions for smoking cessation in SMI. Following a successful open trial of a 52-week maintenance intervention,⁷¹ Drs. [name] and [name] recently completed the first RCT of maintenance smoking cessation treatment in schizophrenia and bipolar disorder (Figure 1). Among 203 smokers, the 43% attaining ≥ 14 -day continuous abstinence at week 12 of an open phase intervention with varenicline and cognitive behavioral therapy (CBT) were randomized to 40 wks varenicline + CBT or placebo +CBT. Maintenance therapy tripled abstinence rates compared to control; 28% of the original sample was abstinent at 1 year (Figure 1).^{61,67} Of those abstinent at week 12, 60% randomized to active treatment were abstinent at 1 year. (data not shown) After discontinuation of pharmacotherapy at 1 year, half relapsed, supporting conceptualization of tobacco dependence a chronic condition in SMI, even after sustained abstinence. This informs our planned 18-month intervention.

[figure not shown]

Figure 1. Maintenance treatment with varenicline+CBT.
First 12 weeks open phase (OP) varenicline +CBT, those abstinent randomized to 40 weeks of varenicline + CBT vs. placebo and CBT for relapse prevention (RP); 52 to 76 weeks followed off treatment.

Dispelling myths about smoking cessation and SMI

Persons with SMI do want to quit smoking. A recent study found 77% of mental health clinicians believe an important barrier to intervention is that SMI patients are not interested in quitting,⁷² however evidence shows the opposite –persons with SMI are at least as likely to want to quit as those in the general population, with 2/3 to 80% wanting to quit.²³ About half want to quit within 6 months and an additional ¼ or more endorse being ready in 30 days²¹⁻²³, categories which essentially correspond to the Transtheoretical Model contemplation and preparation stages.⁷³⁻⁷⁵ Yet, few providers ask patients about smoking cessation or feel comfortable providing it, contributing to the abysmally low rates of receiving guideline-concordant treatment in SMI.^{72,76-79} The proposed trial will test and implement comprehensive smoking cessation treatment in the community.

Pharmacotherapy for smoking cessation is safe in SMI

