Pharmacotherapy for smoking cessation in SMI is universally recommended, but infrequently used in most settings.^{12,72} The study physician(s) are trained education on use, risks, benefits and monitoring of pharmacotherapeutic cessation aids in SMI, and will prescribe and monitor medications for intervention participants, coordinating with and supported by others on the study team. These psychiatrists will discuss medication choice with participants and take their preferences into account while assessing clinical appropriateness for varenicline+/-NRT, and bupropion+NRT (patches with lozenges/gum) Varenicline has been associated with higher abstinence,^{67,203,204} so we expect it will be used preferentially. We will use standard dosing for varenicline and bupropion. Varenicline dosing is 0.5mg for 3 days, 0.5 mg bid for 4 days and then 1mg bid. Subsequent prescriptions are 1mg po bid. Varenicline will be provided by Pfizer. Bupropion is 150mg pod bid SR formulation. Those with adverse effects with varenicline limiting tolerability will be offered a lower dose, or bupropion+NRT. Bupropion+NRT will be offered to those with varenicline contraindications, and vice versa. Once initiated, the goal will be for participants to use medication for the study duration for sustained abstinence, however, if needed they may stop and then resume medication or switch therapies. This flexible approach should improve cessation rates. Physician study visits for smoking cessation pharmacotherapy are separate from the participants' regular mental health visits. Participants will continue to see their regular psychiatrist for mental health care. The physicians prescribing smoking cessation pharmacotherapy will be study team members and will communicate with the participants' regular psychiatrists about the intervention, but will not deliver regular mental health care.

Exercise program. Three approaches will enable participants to achieve 150 mins/week of moderate intensity

Protocol: Trial of Integrated Smoking Cessation, Exercise and Weight Management in SMI

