13. DATA ANALYSIS

Primary Outcome: The primary outcome will be 7-day point prevalence smoking abstinence at 18 months, defined as self-report of 7 days of not smoking, confirmed by expired CO <8ppm with a Bedfont Smokerlyzer II.^{148,153,218 182} Biochemical verification with available urine cotinine (if not on NRT) and/or anabasine will be used as needed to verify self-reported abstinence, particularly if the validity of CO is expected to be low (e.g. COPD or difficulty forming an adequate seal on the smokerlyzer); and if CO is greater than 8 as this could be from second hand smoke or smoked cannabis.¹⁴⁸⁻¹⁵⁰

7-day smoking abstinence at 6,12 and 15 mo. are secondary outcomes.

Other Secondary outcomes focus on AHA metrics for health risk behaviors²⁰² and include: a) continuous abstinence with 1) % continually abstinent over 3 mo. (based on self-reports of abstinence since last visit, using timeline follow-back²¹⁹, and biochemical verification at 15 and 18 month visits), 2) total days abstinent in the study with the same method, b) Weight and BMI; c) Physical fitness with 6-minute walk;¹⁵⁴⁻¹⁵⁶ and d) Healthy diet.¹⁶⁰ We will assess 10-year probability of a CVD event with the global Framingham Risk Score (FRS) incorporating smoking, total and HDL-cholesterol, systolic blood pressure and diabetes mellitus.²²⁰ Others include: health status (SF-12)¹⁶²; Quality of life (Euroqol);¹⁶³⁻¹⁶⁵ psychiatric symptoms (BPRS);¹⁷⁰ ED use and hospitalizations.

We will also examine the difference of mean CO change over time between intervention arms, and, among continuing cigarette smokers, change of mean number of cigarettes smoked per day over time between intervention arms.

For the primary outcome, we will also perform sensitivity analyses using expired CO<6ppm for abstinent confirmation, as this cutpoint has become more acceptable during the time the trial has been implemented.¹⁵⁰ The outcome using this alternative definition will be modeled in the same fashion.

Our recruitment goal is 220 participants will be recruited from 2 community mental health organizations, enrolled, and randomized in equal allocation to active intervention (Group B) and control (Group A), stratified

Protocol: Trial of Integrated Smoking Cessation, Exercise and Weight Management in SMI

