Cost Analysis (Aim 4) will be conducted primarily from an adopting organization or payer's perspective (e.g., Medicaid) estimating incremental intervention implementation costs relative to control. Resource measurement will focus on sampling and tracking intervention staff time. We will sample at specified intervals for 1 week at a time. Tracking specific tasks will allow us to eliminate time spent strictly on research and perform sensitivity analyses with different potential levels of efficiency (e.g., amount of active client involvement vs. administrative time). We will use medication data and data on MD visits and hospitalizations to calculate cost per participant and total costs. With estimates of total costs, we will estimate incremental intervention costs and incremental costs per incremental improvement in 1° and 2° outcomes. To extend the time horizon forward, we will use the global FRS to project the proportion expected to have a CV event within 10 years and the present value of costs and QALYs associated with events, allowing us to perform a societal perspective cost-utility analysis.²²⁶ For all analyses, we will conduct univariate sensitivity analyses by varying assumptions and assess estimate uncertainty by bootstrapping for 10000 replications, drawing samples with replacement where samples have the same number of observations as the main study.²²⁷

Qualitative Analysis (Aims 5-6): Interviews will be transcribed and coded. NVivo will be used to enter and group discrete passages from data into themes. We will use the constant comparative method²²⁸ to categorize transcript statements that demonstrate common attributes, then combine categories into broader, recurrent themes using a hybrid approach where we will start with larger categories and then add nodes and subnodes as new concepts emerge until saturation of ideas is reached. Findings will be shared with study sites and the Advisory Committee to inform ongoing implementation and future sustainability and dissemination.

Power analyses: Under a conservative set of assumptions, this trial with sample size of 220 will have ≥80% power to detect a clinically meaningful effect in our primary outcome of 7-day point prevalence smoking abstinence at 18 months between intervention and control (Table 5). We assume:

1. Two-sided alpha =0.05.

2. Follow-up for primary outcome=100%. In smoking cessation trials, those lost to follow-up are classified as

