Varenicline was effective and well tolerated for long-term abstinence in trials that tested the use of varenicline for 12 months.^{67,223,267} A long-term safety trial found 12-months treatment with varenicline vs. placebo was well tolerated and highly effective for smoking cessation throughout the 52-week treatment period, with a 53-week follow-up RR for seven-day point prevalence abstinence of 4.91 (95%CI 2.56 to 9.42).²⁶⁷ Varenicline was well tolerated in a trial of 52 weeks maintenance therapy with varenicline or placebo in a group of adults with schizophrenia spectrum or bipolar disorder who were able to attain abstinence during a 12-week open-label phase with varenicline and CBT.⁶⁷ In this trial 43% attained abstinence with open smoking cessation treatment, and those assigned to varenicline maintenance treatment had higher abstinence rates at every post randomization visit through 40 weeks of relapse prevention treatment and 24 weeks of follow up. Maintenance treatment tripled both point prevalence and continuous abstinence rates at week 52. Those assigned to maintenance treatment with placebo had a median time to relapse of < 4 weeks while those assigned to varenicline had a median time to first lapse or relapse of 24 weeks. During the follow up phase of the maintenance treatment trial, although 68% of those randomized to varenicline remained abstinent on varenicline at week 52, half of these relapsed during the first three months after discontinuation of maintenance treatment. This trial showed that behavioral treatment alone is not sufficient to maintain abstinence in those with schizophrenia or bipolar disorder who attain abstinence with 12-weeks of pharmacotherapy and CBT, and that even after one year of abstinence, a substantial portion of those who maintained abstinence relapse after treatment discontinuation. This is in line with high early relapse rates reported immediately following discontinuation of pharmacotherapy with bupropion + NRT in adults with schizophrenia.⁵¹ It is also in line with results of varenicline for smoking cessation in 60 outpatient smokers with stable treated bipolar disorder, 15/31

Protocol: Trial of Integrated Smoking Cessation, Exercise and Weight Management in SMI

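### The 10-year cost-utility projection rests on month-18 smoking status, when participants are meant to be still on cessation medication, and applies neither relapse nor medication cost after that point

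*Combined protocol and SAP*

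**What the plan says.** Section 13, Cost Analysis (Aim 4), extends the time horizon as follows: "we will use the global FRS to project the proportion expected to have a CV event within 10 years". The present value of costs and QALYs attached to those events then feeds a societal cost-utility analysis. The FRS is listed in Sections 7 and 13 as including smoking, total and HDL cholesterol, systolic blood pressure and diabetes.

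Table 2 in Section 7 shows fasting blood at baseline and month 18 only, and the visit schedule ends at month 18. The protocol notes confirm that 24-month data were not obtained. Month 18 is also the end of the intervention. On medication, Section 10 says that "the goal will be for participants to use medication for the study duration for sustained abstinence", while allowing participants to stop, resume or switch. Section 16 describes pharmacotherapy of up to 18 months.

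On what happens when medication ends, Section 3 says of the maintenance trial in schizophrenia and bipolar disorder: "After discontinuation of pharmacotherapy at 1 year, half relapsed". Section 16 says of those still abstinent on varenicline at week 52 of that trial that "half of these relapsed during the first three months after discontinuation of maintenance treatment". Section 16 also reports 50% relapse within three months of stopping among abstainers in a 12-week bipolar trial.

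The cost paragraph promises univariate sensitivity analyses and 10,000 bootstrap replications. It does not mention relapse, durability of abstinence, or medication cost after month 18.

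**The concern.** The protocol uses the relapse evidence to justify treating for 18 months, but not when it looks ten years past the end of treatment. Taken literally, the cost paragraph credits end-of-treatment abstinence over the whole horizon. If medication stops at month 18, some of that abstinence is likely to be lost and the smoking-driven benefit is too large. If medication continues, the benefit may hold, but someone pays for it and no such cost is named. Both gaps favour the intervention.

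Aim 4 is meant to inform an adopting organization or payer such as Medicaid, so the cost per QALY is the figure at stake. The primary test of 18-month abstinence is not affected.

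**Working it through.** **Inputs.** Section 13, Power analyses: "Two-sided alpha =0.05"; "220 participants will be recruited from 2 community mental health organizations, enrolled, and randomized in equal allocation", so 110 per arm; "Follow-up for primary outcome=100" per cent; control abstinence 3-5%; active abstinence 17.5-21.5%. Relapse after stopping: 50% (Sections 3 and 16). No CV-event or QALY benefit is stated anywhere, so the abstinence rates are the only planned figures to work from.

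**Step 1: confirm the rates.** Exact power of the two-sided Fisher test, 110 per arm, with active rates of 17.5, 18, 19, 20 and 21% (the 50/50 stratum averages described in the Table 5 footnote) against 5% control, gives .81, .84, .88, .91 and .94. Table 5 prints .80, .83, .87, .91 and .94. All 15 cells agree within 2 points. The 19% and 19.6% printed in the first two columns of row C are 60/40 averages (0.6×25 + 0.4×10; 0.6×26 + 0.4×10), but the powers match 17.5% and 18%, so 17.5% is the right lower rate to use.

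**Step 2: abstinence difference.** Before relapse, d = pA − pC: 17.5 − 5 = 12.5 points at the low end and 21.5 − 3 = 18.5 at the high end. After relapse fractions rA and rC, d′ = pA(1 − rA) − pC(1 − rC). The overstatement is d/d′.

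| Scenario | 17.5% vs 5% | 21.5% vs 3% |
|---|---|---|
| Half relapse in both arms | 12.5/6.25 = 2.0 | 18.5/9.25 = 2.0 |
| Half of active quitters relapse, no control quitters | 12.5/(8.75 − 5) = 12.5/3.75 = 3.3 | 18.5/(10.75 − 3) = 18.5/7.75 = 2.4 |
| Only half of active quitters on medication, so rA = 0.25; no control relapse | 12.5/(13.125 − 5) = 1.5 | 18.5/(16.125 − 3) = 1.4 |

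**Step 3: from abstinence to the FRS.** Let s be the share of the between-arm FRS difference due to smoking and f the fraction of the abstinence contrast lost. If the other components persist, the overstatement of the whole FRS difference is 1/(1 − s·f). From Step 2, f = 0.5 when both arms halve and reaches 1 − 3.75/12.5 = 0.7. The documents do not give s, so it is varied:

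- s = 1: 2.0 to 3.3
- s = 0.75: 1.6 to 2.1
- s = 0.5: 1/(1 − 0.25) = 1.3 to 1/(1 − 0.35) = 1.5
- s = 0.25: 1.1 to 1.2

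**Step 4: a rough check on s.** Section 1 gives smokers with SMI a 40% higher 10-year CVD probability than non-smokers with SMI. Assume a mean 10-year risk in smokers of 8-20% (not in the documents). Quitting then lowers risk by R(1 − 1/1.4) = 0.286R. Across the planned abstinence differences this is worth 0.125 × 8 × 0.286 = 0.29 to 0.185 × 20 × 0.286 = 1.06 FRS points. Section 13 gives 1.2% as the minimal detectable FRS reduction, read here as percentage points. If the total effect were 1.2 points, smoking would supply 24-88% of it, and losing half the abstinence contrast would overstate the total 1.1- to 1.8-fold.

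**The case against.** The cost paragraph is a short summary, and silence is not a decision. It promises to vary its assumptions, and durability could be one of them. It does not name the visit whose FRS is used; month 18 is inferred from the schedule. This carries weight: the fault is an unstated assumption rather than a declared one. But a one-way sensitivity analysis leaves the headline projection as it was, and the bootstrap measures sampling error in observed data, which include no period after the programme ends.

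A reader might infer that projected CV and QALY benefit is overstated 2- to 3-fold. The documents do not support that. It would require every active-arm abstainer to be on medication at month 18 and then stop, although Section 10 allows earlier stopping and nothing rules out continuation through usual care. It would require lasting relapse, although Section 3 expects repeated attempts. It would also require smoking to drive the entire FRS difference, in a trial that also targets weight and exercise. Factors above 2 further assume that control quitters relapse less, while Section 13 allows that controls may obtain medication elsewhere.

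A reader might also infer that seven days of abstinence earns full non-smoker credit, set against Section 3's statement, "After only 1 year of abstinence, myocardial infarction risk is reduced by 50" per cent. The documents say only that the FRS incorporates smoking; neither the coding nor the abstinence definition that enters it is given.

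Finally, the 50% comes from earlier trials of 12 weeks or about a year of treatment. It is not the protocol's forecast for its own participants after 18 months of combined support.

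**Conclusion.** The omission is clear and its likely direction favours the intervention; its size is uncertain. The 2.0-fold and 2.4- to 3.3-fold figures describe the abstinence difference only. They rest on 50% relapse among quitters who were all on medication, and the higher range also on no control relapse. With half of active quitters on medication, the factor falls to about 1.4-1.5. Carried to the FRS, and so to CV events and QALYs, it is about 1.3-1.5 if smoking supplies half of the difference, and approaches the abstinence-scale figures only as that share nears one. Larger factors are possible if relapse continues beyond three months or other FRS inputs worsen after quitting. This is a worthwhile correction to a secondary economic aim.

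**What to change.** In Section 13, Cost Analysis, report the 10-year projection with a post-treatment relapse fraction applied to 18-month abstainers, for example 0%, 25%, 50% and 75%, set separately by arm, with 50% anchored to the trials cited in Section 16. Label strongly asymmetric cells as bounds: at the lowest planned active rate, 75% relapse in the active arm alone gives 17.5 × 0.25 − 5 = −0.6 points. Beside these, show a modelling scenario in which abstinence is maintained by continued medication, with its cost charged over the horizon. Do not present the no-relapse projection as the only base case.

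Tabulate 18-month abstainers by current cessation-medication use, from the medication data that Table 2 already schedules at month 18, to inform the relapse input.

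The cost is a few lines of text and some extra model runs, with no new data. The price is a less favourable cost per QALY.
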